10.3.3. Recording and Follow-Up of AEs and/or SAEs

AE and SAE Recording

- When an AE or SAE occurs, it is the responsibility of the investigator to review all documentation (eg, hospital progress notes, laboratory reports, and diagnostics reports) related to the event.
- The investigator will then record all relevant AE or SAE information in the eCRF.
- It is **not** acceptable for the investigator to send photocopies of the participant's medical records to the sponsor in lieu of completion of the AE or SAE eCRF page.
- There may be instances when copies of medical records for certain cases are requested by the sponsor. In this case, all participant identifiers, with the exception of the participant number, will be redacted on the copies of the medical records before submission to the sponsor.
- The investigator will attempt to establish a diagnosis of the event based on signs, symptoms, and/or other clinical information. Whenever possible, the diagnosis (not the individual signs/symptoms) will be documented as the AE/SAE.

Protocol MT10109L-004 AMD 5

Assessment of Intensity			
MILD	A type of adverse event that is usually transient and may require only minimal treatment or therapeutic intervention. The event does not generally interfere with usual activities of daily living.		
MODERATE	A type of adverse event that is usually alleviated with additional specific therapeutic intervention. The event interferes with usual activities of daily living, causing discomfort but poses no significant or permanent risk of harm to the research participant.		
SEVERE	A type of adverse event that interrupts usual activities of daily living, or significantly affects clinical status, or may require intensive therapeutic intervention.		

An event is defined as *serious* when it meets at least one of the predefined outcomes as described in the definition of an SAE, NOT when it is rated as severe.

Assessment of Causality

- The investigator is obligated to assess the relationship between study intervention and each occurrence of each AE or SAE.
- A *reasonable possibility* of a relationship conveys that there are facts, evidence, and/or arguments to suggest a causal relationship, rather than a relationship cannot be ruled out.
- The investigator will use clinical judgment to determine the relationship.
- Alternative causes, such as underlying disease(s), concomitant therapy, and other risk factors, as well as the temporal relationship of the event to study intervention administration will be considered and investigated.
- The investigator will also consult the IB and/or product information, for marketed products, in his/her assessment.
- For each AE or SAE, the investigator must document in the medical notes that he/she has reviewed the AE or SAE and has provided an assessment of causality.
- There may be situations in which an SAE has occurred and the investigator has minimal information to include in the initial report to the sponsor. However, it is very important that the investigator always make an assessment of causality for every event before the initial transmission of the SAE data to the sponsor.
- The investigator may change his/her opinion of causality in light of follow-up information and send an SAE follow-up report with the updated causality assessment.

[figure not shown]
Protocol MT10109L-004 AMD 5

• The causality assessment is one of the criteria used when determining regulatory reporting requirements.

Follow-up of AEs and SAEs

• See Section 8.3.3

10.3.4. Reporting of SAEs

- is acceptable with a copy of the SAE form, sent by overnight mail or courier service.
- Initial notification via telephone does not replace the need for the investigator to complete and sign the SAE form within the designated reporting time frames.
- •

Protocol MT10109L-004 AMD 5

10.4. Appendix 4: Abbreviations

AE adverse event

AESI adverse event of special interest

ANCOVA analysis of covariance
BoNT/A botulinum toxin type A

CFL crow's feet lines

CFR Code of Federal Regulations

CIOMS Council for International Organizations of Medical Sciences

DVD digital versatile disc ECG electrocardiogram

eCRF electronic case report form

ELISA enzyme-linked immunosorbent assay

EU European Union

FDA US Food and Drug Administration

FSH follicle-stimulating hormone

GCP Good Clinical Practice

GL glabellar lines

HIPAA Health Insurance Portability and Accountability Act

HRT hormonal replacement therapy

IB investigator's brochure ICF informed consent form

ICH International Council for Harmonisation

IEC institutional ethics committee

IM intramuscular

IND investigational new drug application

IRB institutional review board

CONFIDENTIAL Protocol MT10109L-004 AMD 5

MT10109L

ISO International Organization for Standardization

ITT intent-to-treat

intrauterine device **IUD**

IUS intrauterine hormone-releasing system

interactive web response system **IWRS**

LCL lateral canthal lines

 LD_{50} median lethal intraperitoneal dose

medical safety physician **MSP**

PRO patient-reported outcome

SAE serious adverse event SAP statistical analysis plan SoA

schedule of activities

SUSAR suspected unexpected serious adverse reactions

TCA trichloroacetic acid

TEAE treatment-emergent adverse event

TESAE treatment-emergent SAE

U unit

UFL upper facial lines

United States US

WOCBP woman of childbearing potential

[figure not shown]
10.5. Appendix 5: Standard Discontinuation Criteria

CDISC Submission Value	CDISC Definition
Adverse event	Any untoward medical occurrence in a participant or clinical investigation subject administered a pharmaceutical product and which does not necessarily have a causal relationship with this treatment. An AE can therefore be any unintended sign (including an abnormal laboratory finding), symptom, or disease temporally associated with the use of a medicinal (investigational) product, whether or not related to the medicinal (investigational) product. For further information, see the ICH Guideline for Clinical Safety Data Management: Definitions and Standards for Expedited Reporting (modified from ICH E2A) Synonyms: side effect, adverse experience. See also serious adverse event, serious adverse experience. (CDISC glossary)
Completed	To possess every necessary or normal part or component or step; having come or been brought to a conclusion (NCI)
Death	The absence of life or state of being dead (NCI)
Disease relapse	The return of a disease after a period of remission
Failure to meet randomization criteria	An indication that the subject has been unable to fulfill/satisfy the criteria required for assignment into a randomized group
Lack of efficacy	The lack of expected or desired effect related to a therapy (NCI)
Lost to follow-up	The loss or lack of continuation of a subject to follow-up
Non-compliance with study drug	An indication that a subject has not agreed with or followed the instructions related to the study medication (NCI)
Other	Different than the one(s) previously specified or mentioned (NCI)
Physician decision	A position, opinion or judgment reached after consideration by a physician with reference to subject (NCI)
Pregnancy	Pregnancy is the state or condition of having a developing embryo or fetus in the body (uterus), after union of an ovum and spermatozoon, during the period from conception to birth. (NCI)
Progressive disease	A disease process that is increasing in extent or severity (NCI)

Protocol MT10109L-004 AMD 5

Protocol deviation	An event or decision that stands in contrast to the guidelines set out by the protocol (NCI)
Recovery	A healing process and/or an outcome implying relative health. The term is typically used in the context of direct and indirect effects of sickness or injury. (NCI)
Screen failure	The potential subject who does not meet one or more criteria required for participation in a trial
Site terminated by sponsor	An indication that a clinical study was stopped at a particular site by its sponsor (NCI)
Study terminated by sponsor	An indication that a clinical study was stopped by its sponsor (NCI)
Technical problems	A problem with some technical aspect of a clinical study, usually related to an instrument (NCI)
Withdrawal by parent/guardian	An indication that a study participant has been removed from the study by the parent or legal guardian
Withdrawal by subject	An indication that a study participant has removed itself from the study (NCI)

10.6. Appendix 6: Study Tabular Summary

Parameter Group	Parameter	Value
Trial information	Trial Title	A Multicenter, Long-term, Open-label Study to Evaluate the Safety of MT10109L (NivobotulinumtoxinA) for the Treatment of Glabellar Lines and Lateral Canthal Lines
	Clinical Study Sponsor	Medytox, Inc.
	Trial Phase Classification	Phase 3
	Trial Indication	Glabellar Lines and Lateral Canthal Lines
	Trial Indication Type	Intervention
	Trial Type	Safety
	Trial Length	Approximately 24 months
	Planned Country of Investigational Sites	United States, Canada, European Union, and Russia
	Planned Number of Participants	Approximately 800 participants
	FDA-Regulated Device Study	No
	FDA-Regulated Drug Study	Yes
	Pediatric Study	No
Participant information	Diagnosis Group	Participants who completed_lead-in Phase 3 studies MT10109L-001 (GL), MT10109L-002 (LCL), MT10109L-005 (GL with or without LCL), and MT10109L-006 (LCL with or without GL)
	Healthy Participant Indicator	No
	Planned Minimum Age of Participants	19
	Planned Maximum Age of Participants	Not applicable (66 years of age for studies in Russia)
	Sex of Participants	Both
	Stable Disease Minimum Duration	Not applicable

Protocol MT10109L-004 AMD 5

Parameter Group	Parameter	Value
Interventions	Investigational Therapy or Intervention	MT10109L (NivobotulinumtoxinA)
	Intervention Type	Drug
	Pharmacological Class of Invest. Therapy	NivobotulinumtoxinA
	Dose Units	4 U per 0.1 mL
	Dosing Frequency	Up to 9 interventions
	Route of Administration	Intramuscular
	Current Therapy or Intervention	Not applicable
	Added on to Existing Interventions	No
	Control Type	None
	Comparative Intervention Name	Not applicable
Trial design	Study Type	Interventional
	Intervention Model	Open-label
	Planned Number of Arms	3
	Trial is Randomized	No
	Randomization Quotient	Not applicable
	Trial Blinding Schema	Open-label
	Stratification Factor	Not applicable
	Adaptive Design	No
	Study Stop Rules	Not applicable

Protocol MT10109L-004 AMD 5

10.7. Appendix 7: Contraceptive Guidance and Collection of Pregnancy Information

10.7.1. Definitions

Woman of Childbearing Potential (WOCBP)

A woman is considered fertile following menarche and until becoming postmenopausal unless permanently sterile (see below).

Women in the following categories are not considered WOCBP:

- 1. Premenarchal
- 2. Premenopausal female with 1 of the following:
 - Documented hysterectomy
 - Documented bilateral salpingectomy
 - Documented bilateral oophorectomy

Note: Documentation can come from the site personnel's review of the participant's medical records, medical examination, or medical history interview.

3. Postmenopausal female

- A postmenopausal state is defined as no menses for 12 months without an alternative medical cause. A high FSH level in the postmenopausal range may be used to confirm a postmenopausal state in women not using hormonal contraception or HRT. However, in the absence of 12 months of amenorrhea, a single FSH measurement is insufficient.
- Females on HRT and whose menopausal status is in doubt will be required to continue to use one of the nonestrogen hormonal highly effective contraception methods from the lead-in study if they wish to continue their HRT during the current study.

Protocol MT10109L-004 AMD 5

10.7.2. Contraception Guidance

Female Participants

Table 10-1 Highly Effective Contraceptive Methods

Highly Effective Contraceptive Methods That Are User Dependenta

Failure rate of < 1% per year when used consistently and correctly

Combined (estrogen- and progestogen-containing) hormonal contraception associated with inhibition of ovulation

- Oral
- Intravaginal
- Transdermal

Progestogen-only hormonal contraception associated with inhibition of ovulation

- Oral
- Injectable

Highly Effective Methods That Are User Independent^a

Implantable progestogen-only hormonal contraception associated with inhibition of ovulation

- IUD
- IUS
- Etonogestrel implant (ie, Nexplanon®)

Bilateral tubal occlusion

Intrauterine copper contraceptive (ie, ParaGard®)

Vasectomized Partner

A vasectomized partner is a highly effective contraception method provided that the partner is the sole male sexual partner of the WOCBP and the absence of sperm has been confirmed. If not, an additional highly effective method of contraception should be used.

Sexual Abstinence

Sexual abstinence is considered a highly effective method only if defined as refraining from heterosexual intercourse during the entire period of risk associated with the study intervention. The reliability of sexual abstinence needs to be evaluated in relation to the duration of the study and the preferred and usual lifestyle of the participant.

^a Typical use failure rates may differ from those when used consistently and correctly. Use should be consistent with local regulations regarding the use of contraceptive methods for participants participating in clinical studies.

Protocol MT10109L-004 AMD 5

Table 10-2 Acceptable Contraceptive Methods

Acceptable birth control methods that result in a failure of more than 1% per year include:

- Progestogen-only oral hormonal contraception, where inhibition of ovulation is not the primary mode of action
- Male or female condom with or without spermicide
- Cap, diaphragm, or sponge with spermicide
- Nonhormonal intrauterine device

A combination of male condom with either cap, diaphragm, or sponge with spermicide (double barrier methods) are also considered acceptable, but not highly effective, birth control methods.

10.7.3. Pregnancy Testing

- Pregnancy testing, with a sensitivity of will be performed according to instructions provided in the pregnancy test kit.
- WOCBP should only be included after a confirmed menstrual period and a negative highly sensitive urine pregnancy test at Day 1 and, if a participant meets retreatment criteria, a negative urine pregnancy test prior to retreatment.
- Additional pregnancy testing is not required during the study intervention period.
- Pregnancy testing will be performed whenever a menstrual cycle is missed or when pregnancy is otherwise suspected.

10.7.4. Collection of Pregnancy Information

Female Participants Who Become Pregnant

- The investigator will collect pregnancy information on any female participant who becomes pregnant while participating in this study. Information will be recorded on the appropriate form and submitted to the sponsor within 24 hours of learning of a participant's pregnancy. The participant will be followed to determine the outcome of the pregnancy. The investigator will collect follow-up information on the participant and the neonate, and the information will be forwarded to the sponsor. Generally, follow-up will not be required for longer than 6 to 8 weeks beyond the estimated delivery date. Any termination of pregnancy will be reported, regardless of fetal status (presence or absence of anomalies) or indication for the procedure.
- While pregnancy itself is not considered to be an AE or SAE, any pregnancy complication will be reported as an AE or SAE. Abnormal pregnancy outcomes (eg, spontaneous abortion, fetal death, stillbirth, congenital abnormalities, ectopic pregnancy) or genetic abnormalities (whether leading to an elective abortion or not) are always considered to be an SAE and will be reported as such. Any poststudy pregnancy-related SAE considered reasonably related to the study intervention by the investigator will be reported to the

[figure not shown]
Protocol MT10109L-004 AMD 5

sponsor as described in Section 8.3.4. While the investigator is not obligated to actively seek this information in former study participants, he or she may learn of an SAE through spontaneous reporting.

[figure not shown]
• Any female participant who becomes pregnant while participating in the study will discontinue study intervention and be withdrawn from the study.

[figure not shown]
Protocol MT10109L-004 AMD 5

[figure not shown]

[figure not shown]

[figure not shown]

[figure not shown]

[figure not shown]

[figure not shown]

[figure not shown]

[figure not shown]

[figure not shown]

[figure not shown]

[figure not shown]

[figure not shown]

[figure not shown]

[figure not shown]

[figure not shown]

[figure not shown]

[figure not shown]

[figure not shown]

Protocol MT10109L-004 AMD 5

[figure not shown]

## 1. Introduction

Study MT10109L-004 is an open-label extension of Studies MT10109L-001, -002, -005, and -006 evaluating long term safety of MT10109L. This statistical analysis plan provides an

expanded and detailed description of the statistical methods presented in the most recent

All safety and efficacy analyses will be integrated analyses that include data from all the preceding pivotal studies (MT10109L-001, -002, -005, and -006) and the extension study (MT10109L-004). Participants can receive up to 3 interventions in the lead-in studies. Data from up to 3 treatment cycles in the preceding studies and data from the treatment cycles in the -004 extension study will be analyzed as outlined in this analysis plan. All participants enrolled in Study MT10109L-004 will be included for analysis, whether they receive study intervention or not. Specifications of tables, figures, and data listings are contained in a separate document.

[figure not shown]
## 1.1. Objectives and Endpoints

Objective Clinical	Statistical	
Category	Category	Estimand/Variable
		the long-term safety of repeat treatments of MT10109L in participants , or both GL and LCL
Safety:	Primary	Variable: Presence of TEAEs
Incidence of		Population: ITT
adverse		Analysis: Categorical descriptive
events		Number and percentage of participants in individual
		categories ○ Participants with ≥ 1qualifying event counted once per individual category
Safety: Vital signs	Primary	
 
Variable: Change from baseline in vital signs at each cycle after intervention and end of study
 

		Population: ITT
		
 
Analysis: Continuous descriptive for baseline, postbaseline, and change from baseline values
 

		N1 = participants with nonmissing values at both baseline and the specified postbaseline analysis visit/timepoint
Safety:	Primary	Presence of binding and neutralizing antibodies
Binding and		Population: ITT
neutralizing antibodies		Analysis: Categorical descriptive

#### Table 1-1Objectives and Endpoints

MT10109L-004

[figure not shown]
## 1.2. Study Design

#### **Overall Study Design:**

- Global, multicenter, open-label, repeat treatment, parallel-group
- Treatment Group: MT10109L administered in the same treatment area(s) with the same number of injections and injection sites as in their lead-in Phase 3 study.
- Study Duration: 24-month treatment period
- Participants ≥ 19 years old who completed Studies MT10109L-001 (GL), MT10109L-002 (LCL), MT10109L-005 (GL with or without LCL), and MT10109L-006 (LCL with or without GL) and meet study entry criteria may receive up to 9 study interventions in Study MT10109L-004
- Approximately 800 participants will be enrolled at approximately 44 global sites
- Based on meeting retreatment criteria for each intervention, the first intervention in this study may occur at the Day 1 visit and the last intervention may occur at the Day 690 visit (30 days prior to Day 720/study exit).
- \_\_\_\_\_\_
- Participants who complete this study will have an exit visit on Day 720.

[figure not shown]

[figure not shown]

[figure not shown]
Statistical Analysis Plan

### MT10109L-004

[figure not shown]
Statistical Analysis Plan

## MT10109L-004

Statistical Analysis Plan

#### MT10109L-004

Adverse events (AEs) will be monitored in-clinic for ≥ 30 minutes after each study intervention,
 at each subsequent scheduled in-clinic or telephone visit, and at any other time an AE is reported.

[figure not shown]

MT10109L-004

## 2. Sample Size Determination

For this long-term follow-up study, no formal statistical power/sample size calculation was used. Approximately 800 participants are anticipated to be rolled-over into this study. This number is estimated from the sample size from the lead-in Phase 3 studies (MT10109L-001, -002, -005,

and -006);

# 3. Statistical Hypotheses

Not applicable.

MT10109L-004

# 4. Populations for Analysis

The analysis populations will consist of participants as defined below:

#### Table 4-1 Analysis Populations

Population	Definition	Study Treatment by Cycle	Lead-in and Extension Study Possible Treatment Regimens
Intent-to-Treat (ITT)	All participants who enrolled in Study MT10109L-004 and received at least 1 intervention (MT10109L or placebo) in their prior Phase 3 study (MT10109L- 001, -002, -005, or -006) or in the current study. Participant data from the current study will be integrated with the corresponding participant data in Studies MT10109L-001, -002, -005, and - 006.		

MT10109L-004

## 5. Statistical Analyses

## 5.1. General Considerations

[figure not shown]
The proportions of participants who achieve the efficacy endpoints will be summarized with frequency tables. The 95% CI for responders will be estimated based on the observed data by intervention group and by treatment cycle. For the US FDA, efficacy analyses will be based on the ITT population.

The safety analyses will be based on the ITT population.

Statistical analyses will be performed using version 9.4 (or newer) of statistical analysis software (SAS) on a Linux operating system.

## 5.1.1. Treatment Group and Treatment Cycles

All safety and efficacy analyses will be integrated analyses that include data from both the leadin studies and the MT10109L-004 extension study, for participants enrolled into the extension study.

A study treatment cycle is considered to start on the day of treatment with study intervention and end on the day prior to the next study intervention or on the study exit day if there are no subsequent interventions. The nomenclature used will be "treatment cycle 1", "treatment cycle 2", "treatment cycle 3", "treatment cycle 4", "treatment cycle 5", "treatment cycle 6", "treatment

cycle 7", "treatment cycle 8", "treatment cycle 9", "treatment cycle 10", "treatment cycle 11", and "treatment cycle 12" for the lead-in and extension study possible treatment regimen cycles.

Demographic and baseline characteristic, disposition, treatment-emergent adverse event (TEAE) for entire study, vital signs, and immunogenicity tables will be summarized under leadin and extension study possible treatment regimens specified in Table 5-3. It will use planned treatment in lead-in study/ planned treatment in extension study for lead-in and extension study possible treatment regimens.

In general, there will be no substitution of missing time or date. However, any partial information will be utilized to its full extent wherever sensible. For example, a medication may be classified as a prestudy medication if the partial information of the medication ending date with only month and year permits a determination that the medication ended prior to the injection date of the study intervention.

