2.1. Study Rationale

The purpose of this open-label, extension study is to evaluate the long-term safety of repeated MT10109L treatment of GL and/or LCL in participants with moderate to severe GL, LCL, or both (GL and LCL) who completed the lead-in pivotal Phase 3 studies (MT10109L-001, -002, -005, and -006) over an additional 24 months.

The clinical development program for MT10109L in the treatment of GL and LCL includes 4 pivotal Phase 3 double-blind, randomized, parallel-group, placebo-controlled, multicenter clinical studies. Each of these studies will provide the primary safety and efficacy data for MT10109L treatment of GL (Studies MT10109L-001 and -005) and LCL (Studies MT10109L-002 and -006). Participants completing these studies will be eligible to enroll into the current 24-month open-label extension study (Study MT10109L-004) and continue their treatment of GL, LCL, or both GL and LCL.

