4.2. Scientific Rationale for Study Design

4.4. End of Study Definition

The end of the study is defined as the date of the last scheduled procedure shown in the SoA for the last participant in the study globally.

A participant is considered to have completed the study if he/she has completed all phases of the study including the last scheduled procedure shown in the SoA.

Protocol MT10109L-004 AMD 5

[figure not shown]
5. Study Population

Participants who complete Studies MT10109L-001 (GL), MT10109L-002 (LCL), MT10109L-005 (GL with or without LCL), and MT10109L-006 (LCL with or without GL) will be eligible to enroll into this 24-month open-label extension study.

Prospective approval of protocol deviations to recruitment and enrollment criteria, also known as protocol waivers or exemptions, is not permitted.

Protocol MT10109L-004 AMD 5

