### 5.2. Participant Dispositions

#### 5.2.1. Disposition and Exit Status

The analysis will be performed using the ITT populations for overall study and by treatment cycle. The lead-in and extension study possible treatment regimens will be used.

The disposition of study participants consists of a summary of the number of participants enrolled and available in the ITT populations by treatment regimen and overall.

Tabulation of the numbers and percentages of participants in each exit status category (ie, AE, pregnancy, lost to follow-up, lack of efficacy, withdrawal by subject, physician decision, death, progressive disease, protocol deviation, noncompliance with study drug, study terminated by sponsor, site terminated by sponsor and other) will be provided for each treatment regimen of each treatment cycle. Discontinued participants will be listed along with the corresponding reason(s) for early withdrawal from the study.

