#### MT10109L-004

This summary will include the incidence of all TEAEs, the incidence of TEAEs related to treatment, the incidence of TESAEs, the incidence of TESAEs related to treatment, the incidence of TESAEs not-related to treatment, AEs that lead to study discontinuation, and death.

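### Lead-in cycles enter the integrated safety tables only for participants who later completed a lead-in study and rolled over, so early-cycle AE results are conditional on that outcome

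*SAP*

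**What the plan says.** Entry depends on the lead-in outcome. Protocol 2.1 states: "Participants completing these studies will be eligible to enroll into the current 24-month open-label extension study". Protocol 5 repeats that people who complete one of the four lead-in studies "will be eligible to enroll into this 24-month open-label extension study".

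The safety set depends on entry. SAP Table 4-1 defines the ITT population as "All participants who enrolled in Study MT10109L-004 and received at least 1 intervention (MT10109L or placebo) in their prior Phase 3 study", or in the current study. SAP 5.1 adds: "The safety analyses will be based on the ITT population".

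Lead-in time is then brought in for that set. SAP 5.1.1 says the integrated analyses "include data from both the leadin studies and the MT10109L-004 extension study, for participants enrolled into the extension study". SAP 1 allows up to 3 lead-in interventions, SAP 1.2 up to 9 in -004, and SAP 5.1.1 numbers the cycles 1 to 12.

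This series feeds the primary AE tables. SAP 5.3.2.1 presents AEs per MT10109L cycle and for the study as a whole. Its overall summary includes "AEs that lead to study discontinuation, and death", and a further table gives TEAEs leading to discontinuation by preferred term. Under SAP 5.2.1, exit-status counts "will be provided for each treatment regimen of each treatment cycle". The visible text has no display of all treated lead-in participants, no sensitivity analysis and no caveat about selection.

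**The concern.** Restricting an extension analysis to enrollees is normal for events after enrolment. The difficulty is applying the restriction backwards. To be counted in a lead-in cycle, a participant must later have survived and completed the lead-in study and then agreed to continue. Anyone who left a lead-in study because of an AE, died in it, or completed it but declined to continue after a bad reaction is missing from both numerator and denominator.

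The two kinds of cycle are therefore not like for like. A cycle given in -004 counts the people who leave -004 during it. A cycle given in a lead-in study cannot count the people who left that study during it. The primary objective is the safety of repeat treatment, and Protocol 2.2 presents completers as contributing up to 3 years of continuous exposure, so early and late cycles will be read side by side. A rise, a fall or a flat line across cycles could reflect selection, repetition or both.

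**Working it through.** **Cycle count.** The plan's own figure reproduces: 3 lead-in + 9 extension = 12 cycles. There is no formal sample-size calculation to reproduce; SAP 2 anticipates about 800 roll-over participants.

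**What cannot appear.** Enrolment requires lead-in completion, and the safety set requires enrolment. Discontinuation from a lead-in study because of an AE is therefore 0 of about 800 by definition, whatever the true rate, and so is death during a lead-in study. If that 0/800 were read as an observed rate, the exact two-sided 95% upper limit would be 1 − 0.025^(1/800) = 0.46%, and the normal approximation in SAP 5.1.5 would give an interval of zero width. Neither bounds the rate among all treated participants.

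**How many might be missing (assumptions).** The documents give neither the lead-in sample size nor the lead-in drop-out. Let d be the share of treated lead-in participants who did not roll over, and q the share of those who left a lead-in study because of an AE. The all-treated number is 800/(1 − d) and the missing discontinuation rate is q × d. The 800 may include participants given placebo in the lead-in, so counts for MT10109L cycles alone could be smaller; the percentages do not depend on this.

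| d (assumed) | All treated | Missing AE discontinuations at q = 10% | Rate |
|---|---|---|---|
| 5% | 842 | about 4 | 0.5% |
| 10% | 889 | about 9 | 1.0% |
| 20% | 1000 | 20 | 2.0% |
| 30% | 1143 | about 34 | 3.0% |

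Over q = 5% to 20% and d = 5% to 30%, the rate runs from 0.05 × 0.05 = 0.25% to 0.20 × 0.30 = 6%.

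**Effect on other AE incidence (assumptions).** The all-treated incidence is p_all = (1 − d) × p_roll + d × p_non. With R = p_non/p_roll, the relative understatement from using rollovers only is d(R − 1)/[1 + d(R − 1)].

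| d | R = 1 | R = 1.5 | R = 3 |
|---|---|---|---|
| 5% | 0 | 0.025/1.025 = 2% | 0.10/1.10 = 9% |
| 10% | 0 | 0.05/1.05 = 5% | 0.20/1.20 = 17% |
| 20% | 0 | 0.10/1.10 = 9% | 0.40/1.40 = 29% |
| 30% | 0 | 0.15/1.15 = 13% | 0.60/1.60 = 38% |

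**Whether cells labelled cycles 1 to 3 must be zero.** They need not be.
- Participants may have had fewer than 3 lead-in interventions, so cycle 2 or 3 can fall in -004.
- SAP 5.1.1 runs a cycle until the next intervention or study exit, and SAP 1 keeps enrollees who are never treated in -004, so the last lead-in cycle can contain a withdrawal from -004.
- An AE that began in the lead-in and later leads to withdrawal from -004 may be counted in its onset cycle.
- AE tables are by MT10109L cycle and lead-in treatment may have been placebo, so a first MT10109L cycle may fall in -004. The table cells that would settle this are not visible, which is not a fault of the plan.

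**The case against.** The strongest reply is that -004 is only a supplement. Protocol 2.1 assigns the primary safety data to the pivotal studies, and Protocol 2.2 says this study adds to them. First-exposure safety in everyone treated belongs to those studies, and the restriction to enrollees is stated openly. This stands as far as it goes: it limits the harm to the programme. It does not correct the -004 tables, which still set lead-in cycles beside extension cycles with nothing in the visible text to show who is missing.

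Four stronger readings are tempting, and the documents do not support them.
- A reader might infer that AE discontinuation in cycles 1 to 3 is zero by construction. Withdrawals from -004 can fall in those cells; only events that end lead-in participation are excluded.
- A reader might infer that lead-in exposure dilutes the whole-study percentage discontinuing for AEs. SAP Table 1-1 counts each participant once per category, and every ITT member is at risk of leaving -004, so adding lead-in cycles does not dilute that percentage.
- A reader might see a contradiction in SAP 1, which says: "All safety and efficacy analyses will be integrated analyses that include data from all the preceding pivotal studies". The same paragraph names the participants enrolled in -004 as the analysis set. The statement concerns which studies contribute, not which participants.
- A reader might take the 3% eyelid ptosis figure in Protocol Table 8-1, assume 80% roll-over among the unaffected and 60%, 50% or 40% among the affected, and compute 0.03r/(0.03r + 0.97 × 0.80) = 2.27%, 1.90% or 1.52%, an understatement of 24% to 49%. This only restates the assumed roll-over rates, uses another product's data, and leaves out the case of equal roll-over, where the bias is nil.

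**Conclusion.** The concern holds in a limited form. The absence of lead-in AE discontinuations and lead-in deaths is certain, because it follows from the entry rule and the ITT definition. The effect on other AE incidence is conditional: understatement if non-rollovers had more AEs, none if they did not. The ranges in the working rest entirely on assumed values of d, q and R, and neither direction nor size can be fixed from the documents. What the tables cannot support as planned is a clean comparison of early with late cycles, since selection on later completion and roll-over is mixed with the effect of repeat treatment. This is a cheap improvement to the plan; the -004 analysis set itself need not be replaced.

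**What to change.** Keep the -004 ITT population as the analysis set and amend SAP 5.1.1, 5.2.1 and 5.3.2.1:

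- **(a)** For MT10109L cycles given in a lead-in study, add a supportive column showing TEAEs, TESAEs, AEs leading to discontinuation and deaths in all lead-in participants who received MT10109L in that cycle, with the number who did not roll over. Group it by lead-in treatment, because non-rollovers have no extension treatment and cannot be placed in the combined lead-in/extension regimens. Define this supportive set in SAP 4.
- **(b)** Report -004 exit status, AE discontinuations and deaths over the period after -004 enrolment, separately from lead-in time.
- **(c)** Label lead-in-cycle results for the enrolled subset as conditional on lead-in completion and roll-over.

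The cost is SAP wording and some extra tabulation from lead-in study data, with no new data collection. Early-cycle rates may look slightly less favourable.
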